5.5 Other Analyses

Administrative analyses of safety data may be performed for regulatory agency review. Descriptive statistics of subject demographic, baseline characteristics, procedure characteristics, medical history will be presented for each analysis subset. the overall study population

5.6 Changes to Planned Analyses

Any changes to the planned statistical analyses made prior to performing the analyses will be documented in an amended Statistical Analysis Plan approved prior to performing the analyses. Changes from the planned statistical methods after performing the analyses will be documented in the clinical study report along with a reason for the deviation.

6 VALIDATION

All clinical data reports generated per this plan will be validated per [90702587](#), Global WI: Clinical Data Reporting Validation.

7 PROGRAMMING CONSIDERATIONS

7.1 Format of Output

Results of analysis will be output programmatically to Microsoft Office® Word documents from SAS with no manual intervention. All output for the final statistical report will be in the form of a Word document containing tables, figures, graphs, and listings, as appropriate.

7.2 Methods for Handling Missing Data

All subjects who are enrolled will be eligible for evaluation, regardless of the treatment that ensues. Handling of dropouts and missing data will depend on their frequency and the nature of the outcome measure. Adjustments for missing outcomes data will be performed if deemed necessary to eliminate or minimize bias and will be described completely. Statistical models that account for censored data will be employed in appropriate circumstances, e.g., for time-to-event outcomes. Outlier values will be evaluated, and values determined to be invalid will be queried. All data will be included in the analysis unless judged to be invalid.

When calculating rates of adverse events for specific time intervals, missing and partial dates will be handled as shown below:

Partial Date Description	Action Taken
Entire onset date is missing	The implant procedure date will be used for

	the onset date.
The month and the day of the month are missing but the year is available	January 1 st will be used for the month and day of the onset date. However, if the imputed date falls before the implant procedure date, then the implant procedure date will be used for the onset date.
Day is missing, but the month and year are available	The 1 st will be used as the day of the onset date. However, if the imputed date falls before the implant procedure date, then the implant procedure date will be used for the onset date.

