6.2. Study Endpoints

Outcomes in HEAL-LAA will be assessed on an intention-to-treat (ITT) basis and an implanted basis. The ITT analysis set includes all subjects who sign an Informed Consent Form approved by the Institutional Review Board (IRB), meet all clinical inclusion and no clinical exclusion criteria, and the WATCHMAN FLX Pro device has been used for treatment and/or attempted to be used for treatment. The implanted analysis set includes ITT subjects who are implanted with the study device in the correct anatomical position (see full definitions within **Table 9-1** and **Table 24-2**).

The trial endpoints are listed below. Measurements will be collected at baseline, pre-implant on the procedure day through discharge, and at 45 days, 6 months, and 12 months after the implant procedure, unless specified otherwise.

The **primary efficacy endpoint** is: The rate of leak >5 mm at 45-day post-implant TEE for the WATCHMAN FLX™ Pro Primary Analysis Subset is less than a performance goal (PG).

The **primary safety endpoint** is: For the evaluable cohort, the composite rate of all-cause mortality, all stroke, systemic embolism, and major bleeding at 6 months for the WATCHMAN FLX™ Pro Primary Analysis Subset is less than a performance goal (PG).

The Primary Analysis Subset consists of data from the initial 500 enrolled subjects.

Additional endpoints will include the following:

The individual components of the composite safety endpoints above will be reported separately in addition to the overall composites.

The following will also be analyzed:

- Death: Cardiovascular/unknown death and non-cardiovascular death
- Stroke: Disabling and non-disabling stroke; ischemic and hemorrhagic stroke
- Bleeding: International Society on Thrombosis and Haemostasis (ISTH) major and non-major clinically significant
 - Procedural bleeding (≤ 7 days post-procedure)
 - Non-procedural bleeding (>7 days post-procedure)

- Device related thrombus
- Pericardial effusion/tamponade requiring pericardiocentesis or surgery to treat
- Device implant success

See full definitions within **Table 24-2**.

Subset Analysis will be analysed per Section **11.3.4**.

7. Study Design

HEAL-LAA is a prospective, post-market, single-arm, multi-center trial evaluating safety and device success of the WATCHMAN FLX Pro closure device in subjects with non-valvular atrial fibrillation (AF).

[figure not shown]

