3.2.2 Statistical Methods

The primary analysis subset with sufficient 6-month follow-up will be eligible for inclusion in this endpoint analysis. The primary analysis subset with sufficient 6-month follow-up will be included in the denominator for the primary safety event rate. Subjects in the primary analysis subset with the occurrence of one of the following events between the time of implant and 6-month following the procedure will be included in the numerator for the primary safety event rate: all-cause mortality, all stroke, systemic embolism, and major bleeding.

A one-sample Z-test will be used to test the assumption that the composite rate of all-cause mortality, all stroke, systemic embolism, and major bleeding at 6 months $\geq 21\%$. The null hypothesis will be rejected if the resulting p-value is less than 0.025.

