7.3 Rules and Definitions

Binary event rates (proportions) will be calculated on a per subject basis.

The number of subjects included in the safety endpoint outcome rates will be based on subjects who have adequate follow-up (see Section **Error! Reference source not found.**) and/or have experienced any CEC-confirmed events.

For baseline categorical variables, “unknown” responses and missing values will not be counted in rate denominators.

The date of last follow-up will be the latest of the following dates for each subject: site-reported adverse event date, CEC-confirmed event date, index procedure date, discharge date, follow-up visit date, and patient withdrawal (defined as: reasons = xx, xx, xx reasons) date from the end of study form.

Days to (event or last known status) = (event or status) date minus procedure date.

Note: subject withdrawal date should always be the last follow-up date and death date should be the subject last follow-up date if the subject didn't withdraw prior to death.

Length of hospital stay = discharge date minus procedure date.

In-hospital event rates are calculated as the proportion of subjects who experience the specified event from index procedure through day of discharge out of all subjects enrolled.

Out-of-hospital event rates are calculated as the proportion of subjects who experience the specified event from the day after discharge through the number of days as specified out of all subjects who were discharged following index procedure and have adequate follow-up or have experienced the event as specified.

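### Incomplete adverse event dates are imputed to the earliest possible day without regard to later event-free visits, which moves late events into early categories; for the 6-month primary composite the effect is conservative

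*SAP*

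**What the plan says.** SAP 7.2 introduces its rule with "When calculating rates of adverse events for specific time intervals, missing and partial dates will be handled as shown below". It covers three cases:

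- Whole date missing: "The implant procedure date will be used for" the onset.
- Only the year known: 1 January "will be used for the month and day of the onset date".
- Month and year known: the 1st "will be used as the day of the onset date".

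In the two partial-date cases the only lower bound is that "if the imputed date falls before the implant procedure date, then the implant procedure date will be used for the onset date". There is no bound at discharge, at a visit or at the last event-free contact, and no upper bound.

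The onset date then feeds several outputs:

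- **Primary safety.** SAP 3.2.2 counts subjects whose event fell "between the time of implant and 6-month following the procedure will be included in the numerator". SAP 7.4 sets the cut-off at day 180 and treats 150 days as adequate follow-up.
- **Bleeding.** Protocol 6.2 splits bleeding at day 7, with the later category listed as "Non-procedural bleeding (>7 days post-procedure".
- **In-hospital rates.** SAP 7.3: "In-hospital event rates are calculated as the proportion of subjects who experience the specified event from index procedure through day of discharge". Out-of-hospital rates start the day after discharge.
- **Time-to-event endpoints.** SAP 5.1 uses Kaplan-Meier estimates.

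Protocol 10.7 requires a safety assessment before discharge, and Protocol 10.8.1 to 10.8.3 require one at 45 days, 6 months and 12 months.

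**The concern.** The rule can contradict the trial's own record. If the safety assessment at a visit found nothing and the event was first reported later, the record places the onset after that visit. The imputed date may still fall before it. The shift is always towards the procedure, so it does not average out.

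Over the whole of follow-up, procedural and in-hospital events can only be overstated, and non-procedural and out-of-hospital events can only be understated. At an intermediate cut-off such as 6 months, a late event can also be added to the rate. Kaplan-Meier curves step too early.

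The direction matters for interpretation. Protocol 4.1.2 cites less non-procedural bleeding as a result for the original device, and Protocol 16.5 names fewer major bleeds as an anticipated benefit. The rule can only flatter late bleeding over 12 months.

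The SAP is also silent on precedence. The CEC reviews bleeding as procedural or non-procedural (Protocol 19.2), and SAP 5.1 lists that split under CEC-adjudicated endpoints. Neither document says which governs when CEC timing and the imputed date disagree.

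**Working it through.** **1. The plan's own figure.** Inputs (SAP 1, safety sample size): expected rate 14%, performance goal 21%, one-sided α 0.025, 485 evaluable subjects, stated power above 95%. With the variance under the null:

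- 1.96 × √(0.21 × 0.79 / 485) = 0.0362
- √(0.14 × 0.86 / 485) = 0.01576
- Power = Φ((0.07 − 0.0362) / 0.01576) = 98.4%

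The exact binomial gives 98.3%. The stated figure is reproduced.

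**2. The rule applied to single cases.**

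| Implant | True onset | Missing | Imputed day | Result |
|---|---|---|---|---|
| 15 Sep 2023 | 15 Aug 2024 (day 335) | month and day | 15+31+30+31+1 = 108 | inside the 6-month window |
| 10 Jan 2024 | 20 Dec 2024 (day 345) | month and day | 0 | procedural, in-hospital, inside the window |
| 5 Mar 2024 | 30 Mar 2024 (day 25) | day | 0 | procedural, in-hospital |
| 5 Mar 2024 | 20 Sep 2024 (day 199) | day | 180 | inside the window |

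A wholly missing date gives day 0 in every case.

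**3. Share of late events that cross a cut-off.** This is an illustration. It assumes implant dates spread evenly over a 365-day year and true onset days spread evenly over the range shown. The last column assumes event-free contacts at days 1, 45 and 180 and floors the imputed date at the day after the last of these before onset.

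| True onset → imputed | Missing | Present rule | With floor |
|---|---|---|---|
| days 181–365 → day 180 or earlier | whole date | 100% | 0% |
| | month and day | 74.5% | 0% |
| | day | 8.0% | 0% |
| days 8–365 → day 7 or earlier | whole date | 100% | 10.6% |
| | month and day | 50.8% | 10.0% |
| | day | 4.1% | 4.1% |

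Hand check of the 74.5%: an event on days 181–365 stays outside the window only if it falls in the next calendar year and 1 January is itself day 181 or later. For an implant on day u of the year, that requires u ≤ 185 and leaves u onset days. The share staying outside is (185 × 186 / 2) / (365 × 185) = 17,205 / 67,525 = 25.5%, so 74.5% move in.

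Hand check of the 10.6%: onsets on days 8–45 are floored at day 2, and 38 / 358 = 10.6%.

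The floor does nothing for a bleed early after discharge with only the day missing, because no scheduled contact lies between.

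**4. Effect on the primary safety test.** At 14%, 485 × 0.14 ≈ 68 events are expected. The test passes with up to 84 events (485 × (0.21 − 0.0362) = 84.3), or 85 if the variance is taken at the observed rate. From exactly 68 true events, 17 extra misdated subjects (18 on the second variance) would turn a pass into a fail. Replacing 14% by 0.14 + k/485 in the power formula:

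| Extra misdated subjects k | Rate | Power |
|---|---|---|
| 0 | 14.0% | 98.4% |
| 2 | 14.4% | 96.8% |
| 5 | 15.0% | 92.6% |
| 10 | 16.1% | 78.5% |

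Each extra event raises the observed rate, so the chance of declaring success when the true rate is 21% or more can only fall.

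**The case against.** The strongest reply is that the rule is deliberately conservative where it counts. In a single-arm trial against a performance goal, moving events earlier can only add to the 6-month numerator. That stands. A reader might infer that the rule threatens the validity of the primary safety conclusion; the documents do not support this.

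The CEC argument also stands in part. One might say that every undated bleed will be reported as procedural. That is not established, because the split is CEC-adjudicated and SAP 7.3 distinguishes site-reported from CEC-confirmed event dates. What remains is the missing statement of precedence, and the site-reported rates of SAP 7.5, where no committee intervenes.

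Rarity is a fair point. The event form captures a date, doubtful values are queried, and an adjudicated major bleed known only by its year would be unusual.

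Three further readings go too far:

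- With an implant on 10 October, a year-only event is dated 1 January, day 83. An event-free contact in early April does not prove that the event lay outside the window. It may show only that onset came after day 150, while the cut-off is day 180 (about 7 April).
- Attempt subjects are not left without an anchor. The SAP refers to the implant procedure, the protocol times the ITT composite from it, and SAP 7.4 counts from the index procedure. This is a matter of wording.
- In-hospital rates are defined in SAP 7.3 but are not listed endpoints.

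Finally, a floor at the last event-free contact treats silence at a visit as proof of no event, and the 6-month contact may be by telephone. An early event missed there would leave the primary composite, in the device's favour. That is a good reason not to replace the rule for the primary test.

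**Conclusion.** The point holds as a minor one. SAP 7.2 can date an event before a visit at which the trial recorded no event, and the error runs in one direction. It distorts the early/late splits and Kaplan-Meier timing. For the primary composite it is conservative and costs some power.

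The size depends on what is missing. A wholly missing date always becomes day 0. A missing day shifts onset by at most 30 days and matters only near a cut-off. The percentages in the working rest on assumed even spreads of implant and onset dates, which the documents do not supply. The number of incomplete dates is not given and is probably small for adjudicated events. The tipping-point analysis in Protocol 11.1.2.3 addresses inadequate follow-up and does not cover misdated events.

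**What to change.** Amend SAP 7.2 before the analyses are run:

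1. Where the CEC has determined an event date or period, that timing prevails over any imputed date.
2. Otherwise, for time-interval rates, the procedural/non-procedural and in-hospital/out-of-hospital splits and Kaplan-Meier estimates, impute the earliest date consistent with the record. It should be no earlier than the day after the last contact documented event-free and no later than the report or resolution date.
3. For the primary safety test, keep the present earliest-date rule as the conservative analysis and report the bounded-date result as a sensitivity analysis.

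The same edit can make clear that the implant procedure date means the index procedure date.

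The cost is a few lines of text and programming; SAP 7.3 already uses discharge and visit dates to derive last follow-up. The downside is reliance on visit reports, including a possible telephone contact at 6 months, to establish that no event had occurred. The change also leaves early post-discharge bleeds with only the day missing as they are now, unless the CEC can time them.

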7.3 Rules and Definitions

Binary event rates (proportions) will be calculated on a per subject basis.

The number of subjects included in the safety endpoint outcome rates will be based on subjects who have adequate follow-up (see Section **Error! Reference source not found.**) and/or have experienced any CEC-confirmed events.

For baseline categorical variables, “unknown” responses and missing values will not be counted in rate denominators.

The date of last follow-up will be the latest of the following dates for each subject: site-reported adverse event date, CEC-confirmed event date, index procedure date, discharge date, follow-up visit date, and patient withdrawal (defined as: reasons = xx, xx, xx reasons) date from the end of study form.

Days to (event or last known status) = (event or status) date minus procedure date.

Note: subject withdrawal date should always be the last follow-up date and death date should be the subject last follow-up date if the subject didn't withdraw prior to death.

Length of hospital stay = discharge date minus procedure date.

In-hospital event rates are calculated as the proportion of subjects who experience the specified event from index procedure through day of discharge out of all subjects enrolled.

Out-of-hospital event rates are calculated as the proportion of subjects who experience the specified event from the day after discharge through the number of days as specified out of all subjects who were discharged following index procedure and have adequate follow-up or have experienced the event as specified.

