- The center will attempt to contact the subject and reschedule the missed visit and counsel the subject on the importance of maintaining the assigned visit schedule and ascertain if the subject wishes to and/or should continue in the study
- A minimum of 3 attempts (i.e., 2 phone calls followed by a certified letter, or other traceable letter, if necessary) should be made to contact the patient or patient's next of kin for each missed follow-up visit and this information should be documented in the subject's medical record or study file.
- Should the subject continue to be unreachable through the 12-month visit, he or she will be considered to have withdrawn from the study with a primary reason of lost to follow-up.

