11.1.2.1. Statistical Hypotheses for the Primary Safety Endpoint

The statistical hypothesis is that the rate of the primary safety endpoint (composite of all-cause mortality, all stroke, systemic embolization, and major bleeding events evaluated at 6 months after the implant procedure for the WATCHMAN FLX™ Pro device Primary Analysis Subset) is less than a performance goal (PG).

The primary safety endpoint is expressed as the proportion of Primary Analysis Subset subjects who experience mortality, stroke, systemic embolization, and major bleeding events within 6 months after the index procedure among all subjects who either experience mortality/stroke/systemic embolization/major bleeding complications within 6 months after the index procedure or are followed for at least 150 days after the index procedure.

The null and alternative hypotheses for the primary safety endpoint are as follows:

$$H_0: P_{\text{Safety}} \geq PG$$

$$H_1: P_{\text{Safety}} < PG$$

where P_{Safety} is the primary safety endpoint rate for the WATCHMAN FLX Pro Primary Analysis Subset and PG is the performance goal.

The analysis set for the primary safety endpoint is the ITT analysis set from the Primary Analysis Subset. This endpoint will also be analyzed for the implanted analysis set.

A one sample z test will be used to test the one-sided hypothesis of the PG for the WATCHMAN FLX Pro device. If the P value from the z test is <0.025 , the rate of the primary safety endpoint for the WATCHMAN FLX Pro Primary Analysis Subset will be concluded to be less than the PG. This corresponds to the one-sided upper 97.5% confidence bound on the observed rate of the primary safety endpoint at 6 months being less than the PG.

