11.1.2.3. Statistical Methods

All enrolled subjects will be eligible for evaluation. Any events or hospitalizations occurring after the index procedure should be entered in the electronic data capture system. Events with onset date starting from the time of the index procedure will be included in the primary endpoint analysis.

Handling of dropouts and missing data will depend on their frequency and the nature of the outcome measure. Sensitivity analyses (e.g., tipping-point analysis) will be performed to assess the impact of subjects with inadequate follow-up (i.e., missing data) on the primary endpoint and to assess the robustness of the conclusion of the primary analysis. Statistical models that account for censored data will be employed in appropriate circumstances (e.g., for time-to-event outcomes). Suspected invalid data will be queried and corrected in the database prior to statistical analysis. Additional information may be found in the Statistical Analysis Plan.

11.2. *General Statistical Methods*

All statistical analyses will be performed using the SAS System software, version 9.2 or later (Copyright[®] 2000 SAS Institute Inc., [name], USA. All rights reserved).

All statistical analyses will be conducted according to applicable Standard Operating Procedures, Work Instructions, and the study-specific Statistical Analysis Plan.

11.2.1. **Analysis Sets**

Analysis sets for the study are listed below.

- Intention-To-Treat (ITT): This population includes all subjects who sign an Informed Consent Form, meet all clinical inclusion and no clinical exclusion criteria, and the WATCHMAN FLX Pro device has been used for treatment and/or attempted to be used for treatment (Implant & Attempt subjects).
- Implanted: This population includes all subjects who sign an Informed Consent Form, meet all clinical inclusion and no clinical exclusion criteria, and who are implanted with the study device in the correct anatomical position (Implant subjects).

11.2.2. **Control of Systematic Error/Bias**

Selection of subjects for enrollment will be made from the Investigator's usual case load. All subjects meeting the eligibility criteria and having signed the ICF will be eligible for enrollment in the study. To control for the potential bias that could be introduced via sponsor classification of adverse events, a Clinical Events Committee (CEC) will adjudicate all major events to be used in the data analyses.

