If new information becomes available that can significantly affect a subject's future health and medical care, that information shall be provided to the affected subject(s) in written form via a revised ICF or, in some situations, enrolled subjects may be requested to sign and date an addendum to the ICF. In addition to new significant information during the course of a study, other situations may necessitate revision of the ICF, such as if there are amendments to the applicable laws, protocol, a change in Principal Investigator, administrative changes, or following annual review by the IRB. The new version of the ICF must be approved by the IRB. Acceptance by Boston Scientific is required if changes to the revised ICF are requested by the site's IRB. The IRB will determine the subject population to be re-consented.

19. Committees

19.1. *Safety Monitoring Process*

The BSC personnel from the Medical Safety and Safety Trial Operation group review safety data as it is reported by the sites throughout the duration of the study. During scheduled monitoring activities, clinical research monitors further support this review through their review of source documents and other data information. The BSC Medical Safety and Safety teams include health care providers with expertise in cardiology and with the necessary therapeutic and subject matter expertise to evaluate and classify the events into the categories outlined above (Section 17).

19.2. *Clinical Events Committee*

A Clinical Events Committee (CEC) will be used in this study. The CEC is an independent group of individuals with pertinent expertise, which reviews and adjudicates important endpoints and relevant adverse events reported by study investigators.

The CEC will review the following events for this study.

- Stroke (disabling and non-disabling; ischemic and hemorrhagic)
- Systemic Embolism
- Pericardial Effusion requiring pericardiocentesis or surgery
- All-cause mortality (cardiovascular and non-cardiovascular)
- Bleeding: ISTH major and non-major clinically significant bleeding including procedural (≤ 7 days post-procedure) and non-procedural (>7 days post-procedure)
- Other events, at the discretion of Boston Scientific

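### SAP 7.3 can count subjects lost before day 150 as event-free in the primary safety denominator: the withdrawal-reason list is blank, and the withdrawal date is always taken as last follow-up

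*SAP*

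**What the plan says.** **Last follow-up date.** SAP 7.3 takes the latest of several dates: site-reported adverse event, CEC-confirmed event, index procedure, discharge, follow-up visit, and "patient withdrawal (defined as: reasons = xx, xx, xx reasons) date from the end of study form". The reason list is an unfilled template field. A note below adds, without exception, that the "subject withdrawal date should always be the last follow-up date".

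**When an unreachable subject becomes a withdrawal.** Protocol 9.3 does not class a subject as lost at a missed visit. It says: "Should the subject continue to be unreachable through the 12-month visit, he or she will be considered to have withdrawn from the study", with loss to follow-up as the primary reason.

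**Who enters the safety denominator.**
- Protocol 11.1.2.1 admits subjects who have a composite event within 6 months "or are followed for at least 150 days after the index procedure".
- SAP 3.2.2 says: "The primary analysis subset with sufficient 6-month follow-up will be included in the denominator for the primary safety event rate". It does not define sufficient.
- SAP 7.4 sets 150 days as adequate follow-up for the 6-month time point, with events counted to day 180.
- SAP 7.3 bases the safety denominators on subjects with adequate follow-up "and/or have experienced any CEC-confirmed events". Its cross-reference for adequate follow-up is broken.

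**Safeguard.** Protocol 11.1.2.3 plans sensitivity analyses, with a tipping-point analysis as the example, "to assess the impact of subjects with inadequate follow-up (i.e., missing data) on the primary endpoint".

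**The concern.** The last follow-up date decides whether a subject without an event is evaluable for the primary safety endpoint. For a subject who simply stops responding, the SAP can replace the last date on which anything was known with an administrative date about a year after the procedure. That subject is then treated as observed and event-free through 6 months, although nothing may have been known after day 45.

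The wording on committee-confirmed events is a second route to the same result. Under Protocol 19.2 the CEC also reviews pericardial effusion requiring pericardiocentesis or surgery, and bleeding described as "ISTH major and non-major clinically significant bleeding including procedural" and non-procedural. A subject with an early non-major bleed who is then lost would enter the denominator under SAP 7.3 as a non-event. Protocol 11.1.2.1 and SAP 3.2.2 would not admit that subject on such an event alone.

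Both routes add incompletely observed subjects as non-events, so both favour meeting the goal. They also weaken the safeguard: a lost subject already derived as adequately followed is not flagged for a tipping-point analysis of inadequate follow-up.

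**Working it through.** **How the rules combine for one subject.** Take a subject seen at day 45, unreachable afterwards, with no recorded event.

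1. Protocol 9.3: considered withdrawn only once unreachable through the 12-month visit (365 ± 30 days).
2. SAP 7.3: last follow-up is the latest listed date. If the form carries the date from step 1, last follow-up falls near day 365.
3. SAP 7.4: that exceeds 150 days, so follow-up is adequate and the subject counts as event-free.
4. Protocol 11.1.2.1: follow-up actually ended at day 45, so the subject should not be in the denominator.

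If the blank list were completed without loss to follow-up, step 2 would fail under the list but still hold under the note. The two would then conflict.

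**Inputs** (Protocol 11.1.2.2; SAP section 1): performance goal p0 = 0.21, expected rate p1 = 0.14, one-sided α = 0.025, 485 evaluable, 3% attrition, 500 enrolled.

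**The plan's own figures.** 485/0.97 = 500. Power of the one-sample z-test with null variance:

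Φ{[(p0 − p1)√n − 1.96√(p0(1 − p0))]/√(p1(1 − p1))} = Φ{[0.07 × √485 − 1.96 × √0.1659]/√0.1204} = 98.4%.

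The exact binomial power of the same rule is 98.3%. Both agree with the stated power above 95%.

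**Pass limit.** The largest event count x with x < n[0.21 − 1.96√(0.21 × 0.79/n)]:

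| n | bound | largest passing count |
|---|---|---|
| 485 | 84.27 | 84 |
| 490 | 85.23 | 85 |
| 495 | 86.19 | 86 |
| 500 | 87.15 | 87 |

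With 15 losses, the verdict depends on the rule only if 85, 86 or 87 events are observed (85/485 = 17.5% to 87/485 = 17.9%).

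**Type I error at a true rate of 21%.** Here k subjects are lost before day 150. If kept, the test uses n = 500 and the limit of 87, but events come only from the 500 − k subjects actually followed, so the error is P(X ≤ 87) with X ~ Bin(500 − k, 0.21).

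| k lost | excluded | kept as event-free |
|---|---|---|
| 5 | 2.51% | 3.27% |
| 10 | 2.49% | 4.18% |
| 15 | 2.46% | 5.28% |

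The last column assumes no events are seen in the lost subjects. If a quarter of their events are seen before loss (15 subjects at 0.25 × 0.21 = 0.0525, added to 485 at 0.21), the figure for 15 is 4.44%.

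**At the expected 14%.** Pass probability is 98.3% for 84/485, and 99.4% for a limit of 87 with 485 observed.

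**Any-committee-event wording.** The documents give no count of such subjects. Added as non-events to 485 observed subjects, one to three leave the limit at 84 (2.46%). Four or five move it to 85 (3.21%).

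**The case against.** **The bias is conditional.** The subject must be silently lost, the form must carry a late date, and the data cut must follow the form. With an earlier cut there is no withdrawal date, and the subject drops out correctly. This is true. The documents fix neither the form date nor the cut, so the rule has to be written to work in either case.

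**The note has an ordinary reading.** It can be taken as precedence: nothing counts after withdrawal, consistent with Protocol 9.2. For someone who withdraws consent at day 60 it gives the right answer. That stands, and it confines the follow-up-date problem to subjects lost to follow-up. For them the note still gives the wrong date.

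**The protocol's intention is clear.** Protocol 11.1.2.1 requires subjects to be followed for 150 days, and an unreachable subject is not being followed. That shows what was meant, but the derivation in SAP 7.3 does not implement it.

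**Missed visits are traceable.** They are recorded as protocol deviations (Protocol 10.8) after at least three contact attempts (9.3), and the 6-month visit may be by telephone. This limits silent loss. It does not place a subject derived as adequately followed into the tipping-point set.

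**Fifteen is an extreme.** It is total planned attrition, and some of those exits would be handled correctly. If only three of the 15 were wrongly kept (n = 488), the limit would stay at 84 and nothing would change. This stands: 5.3% is an upper bound within planned attrition.

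**The any-committee-event wording is loose drafting.** SAP 7.3 itself uses narrower wording for out-of-hospital rates. That is plausible, and the likely effect is small, but as written it contradicts the protocol's denominator.

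**Conclusion.** The concern holds and should be fixed before analysis. SAP 7.3 does not reliably yield the denominator defined in Protocol 11.1.2.1: its stated rules, not only the blank field, can admit subjects without 150 days of observation as non-events.

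The size is modest. Within planned attrition the one-sided type I error lies between 2.5% and 5.3%, depending on how many subjects are affected and how many of their events are seen before loss. The verdict changes only within a three-event band. If the true rate is near the expected 14%, the trial very probably passes under either rule.

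These figures assume a null-variance z-test and that lost subjects share the 21% rate of the others. The follow-up-date figures also assume that the End of Study form carries a date past day 150 and that the data cut follows it; the documents settle neither point. Confidence in the practical effect is therefore medium. Confidence that the text needs repair is higher, because completing the list without loss to follow-up would leave it in conflict with the note.

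**What to change.** In SAP 7.3:

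1. For subjects who exit as lost to follow-up, set last follow-up to the last documented contact, visit or event date. Use the withdrawal date only where the subject was in contact on that date. Complete the reason list, and reword the note so that it no longer applies to every withdrawal.
2. For the primary safety endpoint, replace the any-committee-event criterion with a component of the primary safety composite within 180 days. Point the broken cross-reference to SAP 7.4.
3. State that subjects then short of 150 days without a composite event go into the tipping-point analysis of Protocol 11.1.2.3.

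The cost is two or three sentences, the corrected reference and one derivation. If the database holds no separate last-contact field, the visit and event dates already listed in SAP 7.3 can serve. The evaluable number falls slightly, to about the 485 already planned. The change should be made before the safety data are analysed, because completing the list afterwards would be a post hoc choice about the primary denominator.
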